Objectives:	The objective of this observational prospective study is to systematically document the clinical outcomes of Zimmer MotionLoc Screws for Periarticular Locking Plate System applied to distal tibia fracture treatment and confirm safety and performance of the screws.
Endpoints:	
Primary endpoint: Radiologic & clinical fracture healing at three months post-surgery.
 
Secondary endpoints:
 
 • Complications • Radiologic & clinical fracture healing at 6 weeks, 3, 6, and 12 months post-surgery. • Callus size & distribution at 6 weeks, 3, 6, and 12 months post-surgery.
Target Population:	Patients with distal tibia fractures (AO 43-A and C) requiring surgical intervention eligible for locked plating.
Study Design:	Prospective, global, multi-center, non-randomized, non-controlled
Number of Cases:	Patient enrollment is limited to one year or 40 subjects whichever is reached first. Per site enrollment will be limited to 15 subjects.
Length of Study:	2 years (1 year enrollment plus 1 year follow-up): Required follow-up visits at 6 weeks, 3, 6, and 12 months post-surgery.
Study Device:	Zimmer® Periarticular Distal Tibial Locking Plates (medial and/or lateral) in conjunction with Zimmer® MotionLoc® Screw for the Periarticular Locking Plate System.
Scores:	FIX-IT
Documentation:	Electronic Case Report Forms
Statistical Reporting:	Data collected will be summarized and reported to each participating investigator. Statistical analysis will be conducted by Zimmer Biomet or its designee.

II. Introduction

The optimal treatment for distal tibia fractures remains controversial. A recent systematic literature review found a reduced risk for malalignment for plate fixation compared to intramedullary nailing [2]. However, for bone union, wound complications and superficial infection or deep infection no statistically significant differences were identified.

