In the last decade locking plates gained popularity not only for distal tibia fractures but fracture treatment in general. Recent studies raised concerns because of the inherent stiffness of these locking devices and found they might suppress fracture healing [3][4][5]. To address this issue the concept of Far Cortical Locking (FCL) was developed [6][7] and has been commercially available since 2010 in the *Zimmer MotionLoc* Screw for NCB[®] Polyaxial Locking Plate System and since 2014 in the *Zimmer MotionLoc* Screw for *Zimmer* Periarticular Locking Plate System (Zimmer Inc.).

FCL screws lock rigidly into the plate and into the far cortex, but retain a controlled motion envelope in the near cortex. The screws have an elastic shaft portion that can deflect within this motion envelope. This flexion of FCL screw shafts induces symmetric axial motion at the fracture site in response to load bearing. FCL screws are optimized to reduce the initial stiffness of a locked plating construct while retaining its construct and fixation strength. *MotionLoc* Screws for *Zimmer* Periarticular Locking Plate System reduce the locked plating construct stiffness by more than 58% while retaining construct strength [8].

Recently, a prospective observational clinical study in 31 distal femur fractures treated with *Zimmer MotionLoc* Screws for NCB Polyaxial Locking Plate System has shown a fracture healing rate of 97% (30 out of 31) after a 6 month follow up period with no implant and fixation failure.

The purpose of this observational prospective study is to systematically document the clinical outcomes of *Zimmer MotionLoc* Screws for Periarticular Locking Plate System applied in distal tibia fracture treatment and confirm safety and performance of the screws.

III. Study Objectives

The objective of this observational prospective study is to systematically document the clinical outcome of *Zimmer MotionLoc* Screws for Periarticular Locking Plate System applied in distal tibia fracture treatment and confirm safety and performance.

Primary Endpoint:

- Radiographic & clinical fracture healing at 3 months post-surgery.

Secondary Endpoints:

- Complications
- Radiologic & clinical fracture healing at 6 weeks, 3, 6, and 12 months post-surgery.
- Callus size & distribution at 6 weeks, 3, 6, and 12 months post-surgery.

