After the initial visit followed by surgery, the patient is expected to participate in the study for a time period of one year. With estimated enrollment duration of one year the estimated overall study duration will be two years.

Study Population

The study population consists of maximally 40 subjects with distal tibia fractures. Subject enrollment is limited to one year or 40 subjects, whichever is reached first. If after one year less than 30 subjects are enrolled, enrollment will be continued until 30 subjects are enrolled.

Number of Subjects, Number of Sites

A maximum of 40 subjects will be enrolled at about 8 study sites. Per site enrollment will be limited to 15 subjects.

VI. Study Procedures

Patient Inclusion / Exclusion Criteria

Inclusion Criteria

- Male and female
- Age: 18 years or older
- Primary distal tibia fractures (AO 43-A and C) requiring surgical intervention eligible for locked plating
- With or without fibula fracture involvement (treated or not treated by osteosynthesis)
- Close or open fractures Gustilo type I
- Unilateral or bilateral fractures
- Patients who are capable of understanding the doctor's explanations, following his instructions and are able to participate in the follow-up program.
- Patients who give written consent to take part in the study by signing the "Patient Consent Form".

Exclusion Criteria

- Delay of surgery for more than two weeks.
- Open fractures Gustilo type II & III
- History of infection of the affected extremity
- Non-ambulatory patients
- Planned fixation strategy includes interfragmentary lag screw fixation of non-articular fractures.
- Addition of bone graft, bone graft substitute or BMP.
- Immobilization with plaster.
- Likely problems with maintaining follow-up program (e.g. patients with no fixed address, plans to move during course of study)
- Not expected to survive the duration of follow-up program.
- Patients known to be pregnant or breastfeeding.
- Patients who are unwilling or unable to give consent.

Product contraindications:

- All concomitant diseases that may impair the fixation of the implant and/or the success of the intervention.
- Acute or chronic, local or systemic infections.
- Severe muscular, neural, or vascular diseases that endanger the extremities involved.
- Lack of bone substance or bone quality, which makes stable seating of the screws impossible or results in an unstable screw/plate construct.
- Allergy to the implanted material.

Patient Screening

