Follow-up evaluations will be performed at 6 weeks (± 14 days), 3 months (± 14 days), 6 months (± 30 days) and 12 months (± 30 days) post-surgery. Standard anteroposterior and lateral x-rays of the operated side must be obtained at each follow-up. If the treating surgeon is unable to adequately assess cortical healing due to radiographic obstruction of the implant(s), additional x-ray(s) should be performed. At 3 months a CT scan of the fracture site must be performed in addition. The “Follow-up” set of forms must be completed at each follow-up time point. This includes the assessment of radiologic fracture healing. At 6 weeks, 3, 6 and 12 months, the surgeon must assess the FIX-IT Score and document on the corresponding set of forms. At the 12

month follow-up the “Study Completion” form must be completed additionally. Copies of the original x-ray films and CT scans must be sent to the Sponsor.

Patient Withdrawal

Patient withdrawal has to be documented on the “Study Completion” form. In particular the reason for withdrawal must be documented. The occurrence of any of the following situations gives reason to withdraw a patient from the study:

- Voluntary patient withdrawal. Patients are at liberty to withdraw from the study at any time and for any reason without affecting future treatment.
- Development of a concurrent condition which would interfere with the patient's continued participation.
- Reoperation including complete removal of study device(s).
- Patient is non-compliant.

Lost to Follow-up

Patients will be considered lost to follow-up after they have missed a visit and a reasonable number of attempts to locate and evaluate them have failed. This has to be documented on the “Study Completion” form and in particular the reason should be documented. Patients lost to follow-up will not be replaced within the study.

Minimization of Subjects Lost to Follow-Up

Subject follow-up is extremely important for the conduct of a clinical study. The expectation is to maintain the highest rate of follow-up compliance possible throughout this study. No replacement is foreseen for any patient lost to follow-up. In an effort to minimize lost-to-follow-up subjects, the following recommendations and/or study requirements are essential to ensure proper patient selection and compliance:

1. Patient Eligibility: Subjects will be selected according to the inclusion/exclusion criteria detailed in Section 8 and are expected to return for all follow-up visits.

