If a device has to be removed¹, the investigator will choose the best revision treatment method for the subject. Before revision surgery, the Investigator must document any significant radiographic findings related to the need for revision. Additionally, once the revision surgery has been completed, the Investigator must complete an Adverse Event CRF, as well as a Study Completion CRF, terminating the subject from the study.

¹Device removal after fracture healing, upon patient request or as part of standard treatment, is not considered a “Recommended Revision Procedure”.

Explanted Device Return

All components removed, except the devices removed after fracture healing upon patient request or as part of standard treatment, should be returned to Zimmer Biomet for analysis. The Investigator must notify the Clinical Study Manager prior to the return of any device. Properly prepared specimens are to be sent to:

Zimmer Biomet
Attention: Product Services Department
[name]
[name]

VII. Statistical Methods

General Statistical Methods

Considering the inclusion and exclusion criteria, per study site an enrollment of 5 patients in one year can be expected. Within one year of enrollment at 8 study sites this equals to 40 patients in total. For the purpose of this observational study this number of patients is considered to be sufficient to document first clinical outcome and assess safety and performance. Collected data will be presented descriptively. For categorical data, frequency and percentage will be calculated. For continuous data, mean, standard deviation, median, minimum and maximum will be calculated.

Comparative assessment

For comparative assessments of any non-parametric data (e.g. score between different follow-up time points) the Wilcoxon test will be used for paired, and the Mann-Whitney test for unpaired data. A significance level of $p=0.05$ will be set.

VIII. Risk Analysis

Zimmer MotionLoc Screws for the *Zimmer* Periarticular Locking Plate System have been commercially available since April 2014. The devices involved are used in accordance with the cleared indications. There are no anticipated risks specific to study participation other than the potential loss of confidentiality. There are no experimental procedures in this study and participation is not anticipated to affect the medical treatment of enrolled subjects.

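### Safety and performance are to be confirmed from bare percentages in 30 to 40 subjects, and nothing keeps early revisions in the 3-month healing denominator

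*Combined protocol and SAP*

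**What the plan says.** **Objective.** The synopsis aims to "confirm safety and performance of the screws". Section III repeats this for the device "applied in distal tibia fracture treatment and confirm safety and performance". The design has one group and no control. The primary endpoint is radiologic and clinical healing at 3 months; complications are secondary.

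**Analysis.** Under General Statistical Methods, Section VII says: "For categorical data, frequency and percentage will be calculated". Continuous data get the mean, standard deviation, median and range. Under Comparative assessment, "the Wilcoxon test will be used for paired, and the Mann-Whitney test for unpaired data", at a 0.05 level, for non-parametric data such as scores at different visits.

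**Sample size.** Section VII multiplies 8 sites by 5 expected patients to reach 40, then states that "this number of patients is considered to be sufficient to document first clinical outcome and assess safety and performance". Section V (Study Population) makes 40 the maximum and adds: "If after one year less than 30 subjects are enrolled, enrollment will be continued until 30 subjects are enrolled".

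**Exits.** Section VI (Patient Withdrawal) lists reoperation with complete removal of the study hardware as a reason to withdraw a patient. Section VI (Recommended Revision Procedure) speaks of removal of a device, without the word complete, and ends the subject's participation after the revision. Its footnote exempts removal once the fracture has healed, if the patient asks for it or it is routine. On losses, Section VI says: "Patients lost to follow-up will not be replaced within the study".

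**The concern.** There are two separate gaps.

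The first is uncertainty. Radiologic healing (three of four cortices bridged, Section III) and each complication are yes/no outcomes. The plan gives each a count and a percentage and nothing else. The rank tests concern scores and say nothing about how well a rate is known. With no interval, target precision or reference rate for 3-month healing, a bare percentage from 30 to 40 subjects cannot carry the word *confirm*.

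The second is the healing denominator. Because of the footnote, participation ended by revision falls mainly on subjects whose fracture has not healed. Such a subject revised before 3 months has no 3-month assessment. If the percentage is taken over subjects assessed at that visit, the failure disappears from the denominator and the rate moves in the device's favour. Section VII names no denominator, so nothing prevents this.

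The results may travel beyond the study: Section VI (Radiographic Management) foresees use of the radiographs in regulatory submissions or product evaluations.

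**Working it through.** **Inputs from the documents.** 8 sites and 5 patients per site per year (Section VII); maximum 40, floor 30 (Section V); losses not replaced (Section VI).

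**Assumed inputs.** The documents give no expected healing, complication or loss rate for this study. All observed counts below, the 20% loss and the two early revisions are assumptions. The one healing rate quoted, 30/31 = 97% in Section II, is for the distal femur, another plate system and 6 months, so it is not a reference for 3-month tibial healing.

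**Step 1: the plan's own figure.** 8 × 5 = 40. It reproduces, as an accrual product; no precision or power enters it.

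**Step 2: precision of a healing rate.** Exact (Clopper-Pearson) two-sided 95% limits for x of n: lower = the 0.025 quantile of Beta(x, n − x + 1); upper = the 0.975 quantile of Beta(x + 1, n − x).

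| Observed rate | n = 40 | n = 30 |
|---|---|---|
| 70% | 28/40: 53.5–83.4% | 21/30: 50.6–85.3% |
| 80% | 32/40: 64.4–90.9% | 24/30: 61.4–92.3% |
| 90% | 36/40: 76.3–97.2% | 27/30: 73.5–97.9% |

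At 80% the interval is 26.6 points wide at n = 40 and 30.9 points at n = 30.

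**Step 3: complications.** With zero events the two-sided 95% upper limit is 1 − 0.025^(1/n):

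- n = 40: 8.8%
- n = 30: 11.6%
- After 20% loss, if only subjects still followed are informative: 10.9% (n = 40 × 0.8 = 32) and 14.2% (n = 30 × 0.8 = 24)

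With two events: 2/40 = 5.0% (0.6–16.9%) and 2/30 = 6.7% (0.8–22.1%).

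**Step 4: the healing denominator.** Suppose two unhealed subjects are revised before 3 months.

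| Implanted | Revised subjects counted as not healed | Revised subjects dropped | Shift |
|---|---|---|---|
| 40 | 32/40 = 80.0% (64.4–90.9%) | 32/38 = 84.2% (68.7–94.0%) | +4.2 points |
| 30 | 24/30 = 80.0% (61.4–92.3%) | 24/28 = 85.7% (67.3–96.0%) | +5.7 points |

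The number healed is the same in each row; only the denominator changes.

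**Step 5: the opposite extreme.** Counting every missing subject as not healed also has a price. With 20% of 40 lost, 32 are assessed. If 26 of them are healed, 26/32 = 81% becomes 26/40 = 65%, a fall of about 16 points. An all-implanted denominator is therefore suitable as a sensitivity rate, not as the main one.

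**The case against.** The strongest reply is that this is an observational study with a descriptive plan and no hypothesis on the rates. Section VII itself claims only to document a first outcome and assess safety and performance; *confirm* appears in the objectives, behind a leading aim of documentation. A reader can compute an interval from printed counts. Much of this stands. A reader might infer that the study needed a powered test or a success criterion; the documents do not support that, and none is asked for here. An interval is itself descriptive, but a reader can derive the right one only if the denominator is known.

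A reader might also infer that the plan removes revised subjects from the healing rate. It does not say so. It is silent, and the number and timing of revisions are unknown and may be zero. Nor do the documents show that every reoperation ends participation: Patient Withdrawal mentions complete removal only, Recommended Revision Procedure speaks of a device, and the two passages need to be reconciled.

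Finally, a reader might extend the denominator argument to complications. That does not hold. Revision requires an adverse event form (Section VI), and complications are documented throughout (Section IX), so the event in a revised subject is recorded. Early failures can be found in the study data. What is missing is a rule for how they enter the healing rate.

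**Conclusion.** The point holds in two limited parts.

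1. The plan attaches no uncertainty to any healing or complication rate, while the objectives speak of confirming. At 30 to 40 subjects, an assumed 80% healing rate is known only to within about 64–91% or 61–92%, and zero events does not exclude a true rate of 8.8% or 11.6% (two-sided 95%). The sufficiency statement rests on accrual and does not address the floor of 30.
2. The 3-month healing denominator is open to losing unhealed subjects whose device was removed early. Two such subjects, an assumed number, would raise an 80.0% rate by 4.2 points (n = 40) or 5.7 points (n = 30). This is a possibility the plan leaves open, not a rule it adopts, and it concerns healing only.

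The absence of intervals and of a healing denominator is certain from the text; the sizes depend on the assumed counts. Neither part invalidates the study. Both can be settled in wording before analysis.

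**What to change.** 1. **Intervals (Section VII).** Report exact two-sided 95% confidence intervals for radiologic healing at each visit and for the proportion of subjects with each complication. Do the same for combined radiologic and clinical healing once its yes/no rule is set: Section III names the ordinal FIX-IT score but gives no threshold.
2. **Denominators (Section VII).**
   - Main healing rate: subjects assessed at the visit plus subjects whose device was removed before healing, the latter counted as not healed. Show the number missing for other reasons.
   - Sensitivity rate: all implanted subjects, with all missing counted as not healed.
   - Count per subject. Bilateral fractures are eligible (Section V), so a bilateral case counts as healed only if both study fractures are healed.
   - Complications: all implanted subjects.
3. **Precision (Section VII).** Replace the sufficiency sentence with what the study delivers: at an assumed 80% healing rate, 64–91% at n = 40 and 61–92% at n = 30; zero-event two-sided 95% upper limits of 8.8% and 11.6%; all wider with losses.
4. **Objectives (synopsis and Section III).** Change *confirm* to *estimate*, in line with the more modest wording of Section VII.

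**Cost.** No extra patients, visits or images: some wording, one interval per rate, and a counting rule fixed before analysis. The limits will look wide, the main healing rate will be slightly lower if early revisions occur, and the sensitivity rate may be much lower if losses are high.

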When used in accordance with product labeling, the risks associated with the used device are similar to those of other locking plate systems used for the same clinical indication or purpose. These risks are either general surgical risks or risks associated with the subject procedure/study device. Unanticipated adverse events can also occur.

A list of adverse events (AE) and anticipated adverse device effects (ADE) can be found in the package insert of the system (see section "Adverse Effects"). Investigators should refer to this list.

All subjects enrolled in the study will have a CT scan of the fracture performed 3 months following surgery. CT scans are frequently used to assess healing because they provide cross-sectional imaging along the entire fracture site; this is particularly useful when orthopaedic implants partially obscure the fracture lines on plain x-ray. In the proposed study, the CT scan will be performed to definitively characterize the healing pattern at the fracture site and to quantify the amount of callus (new healing bone) present. As a result, all subjects will be exposed to the radiation associated with the CT scan of the tibia fracture site at 3 months. The effective dose of radiation from a CT scan of the ankle area is 0.16 ± 0.12 mSv. This is equivalent to two chest x-rays and is a fraction of annual background natural radiation exposure (3 mSv) [14].

Management of Incurrent Events

Any adverse events that occur during the clinical study must be reported to Zimmer Biomet, whether they are device-related or not.

Adverse Events

An Adverse Event (AE) is any untoward medical occurrence, unintended disease or injury, or untoward clinical signs (including abnormal laboratory findings) in subjects, users or other persons, whether or not related to the investigational medical device.

Notes:

- This definition includes events related to the investigational medical device or the comparator.
- This definition includes events related to the procedures involved.
- For users or other persons, this definition is restricted to events related to investigational medical devices.

Serious Adverse Events

A Serious Adverse Event (SAE) is any AE that:

- led to death,
- led to a serious deterioration in the health of the subject that either resulted in
 1. a life threatening illness or injury,
 2. a permanent impairment of a body structure or body function, or
 3. in-patient or prolonged hospitalization, or

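### Complications are to be summarised only by frequency and percentage, with no stated denominator and no method for subjects who leave before 12 months

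*Combined protocol and SAP*

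**What the plan says.** Section III lists complications as a secondary endpoint ("Secondary Endpoints: - Complications") without a time point, unit of analysis or denominator. The healing and callus endpoints beside it carry visit times.

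Section VII, General Statistical Methods, says "Collected data will be presented descriptively", and then "For categorical data, frequency and percentage will be calculated". Nothing there or elsewhere gives a time-to-event method, a person-time rate, an analysis population or a missing-data rule.

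Collection is continuous over follow-up. Section V (Study Duration) says "the patient is expected to participate in the study for a time period of one year", and Section VIII (Management of Incurrent Events) says "Any adverse events that occur during the clinical study must be reported to Zimmer Biomet". Section IX keeps the Complication form open throughout the study.

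Follow-up can end early. Section VI (Patient Withdrawal) allows exit for voluntary withdrawal, an interfering condition, non-compliance, or a reoperation that removes the device completely. Under Lost to Follow-up it adds: "Patients lost to follow-up will not be replaced within the study". Under Recommended Revision Procedure, a revised subject has an Adverse Event CRF completed and is then terminated from the study.

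On size, Section V says "A maximum of 40 subjects will be enrolled at about 8 study sites" and "If after one year less than 30 subjects are enrolled, enrollment will be continued until 30 subjects are enrolled".

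**The concern.** Confirming safety is part of the stated objective, and the complication percentage will be its main numerical expression. When complications accrue over a year and some subjects are seen for only part of it, one percentage can mean several things. It may be the share of everyone treated who was seen to have a complication, the share among those who finished, or something between. These differ in value, and not all in the same direction. Because the plan does not choose, the choice can be made after the data are seen.

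A percentage that ignores time at risk also has no clear horizon. The only clinical series described in the Introduction (31 distal femur fractures) reports at 6 months, whereas this study runs to 12. An estimate indexed to 3, 6 and 12 months would let a reader see which period a figure covers.

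**Working it through.** **The plan's own figure.** The only calculation in Section VII is recruitment: 8 sites x 5 subjects per site in one year = 40, which reproduces. There is no power or precision calculation, expected complication rate or expected dropout rate.

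**Inputs.** From the documents: 12 months of follow-up, 30 to 40 subjects, no replacement of those lost. Assumed, because the documents do not give them: 12-month risk of a first complication R of 20% or 30%, and dropout by 12 months d of 10%, 20% or 30%, unrelated to complications.

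**All enrolled as denominator, constant hazards.** Let h = -ln(1 - R) and g = -ln(1 - d), per year. The expected percentage is

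h/(h + g) x (1 - exp(-(h + g))).

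At R = d = 20%, h = g = 0.2231, so the result is 0.5 x (1 - 0.8 x 0.8) = 18.0%, a shortfall of 2.0 points.

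**Events early.** If all complications fall in the first 3 months, h is replaced by H = h/0.25 and the formula is run over 0.25 years: H/(H + g) x (1 - exp(-0.25(H + g))). At R = d = 20% this gives 19.5%.

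**Subjects with events plus event-free completers as denominator.** Event-free completers are (1 - R)(1 - d) of all subjects. At R = d = 20%, constant hazards, this gives 0.18/(0.18 + 0.64) = 22.0%.

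| True risk | Dropout | All enrolled, constant hazards | Shortfall (points) | All enrolled, events in first 3 months | Events plus event-free completers |
|---|---|---|---|---|---|
| 20% | 10% | 19.0% | 1.0 | 19.7% | 20.9% |
| 20% | 20% | 18.0% | 2.0 | 19.5% | 22.0% |
| 20% | 30% | 16.9% | 3.1 | 19.2% | 23.2% |
| 30% | 20% | 27.1% | 2.9 | 29.2% | 32.6% |
| 30% | 30% | 25.5% | 4.5 | 28.8% | 34.2% |

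**A second dropout model.** With departures spread evenly over the year and a constant complication hazard, the expected percentage is R(1 - d) + d(1 - R/h).

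- R = d = 20%: 0.16 + 0.2 x (1 - 0.2/0.2231) = 18.1%.
- R = d = 30%: h = 0.3567, and 0.21 + 0.3 x (1 - 0.3/0.3567) = 25.8%, a shortfall of 4.2 points.

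The size hardly depends on which of the two dropout models is used.

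**Completers only.** If dropout were unrelated to complications, this would return the true risk: at R = d = 20%, 16 events among 80 completers per 100 enrolled, or 20.0%. In this study some exits are caused by the event, because a revised subject is terminated. As an illustration, take 8 of 40 subjects with a complication, 2 of them revised and terminated, and no other exits. Completers only gives 6/38 = 15.8%, against 8/40 = 20%.

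**Scale.** Exact (Clopper-Pearson) 95% intervals are 9.1% to 35.6% for 8/40 and 7.7% to 38.6% for 6/30. One subject in 40 is 2.5 points.

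**The case against.** A reader might infer that the plan counts everyone who leaves early as free of complications for the whole year, and so reports a rate that is too low by design. The documents do not support that. The sentence in Section VII is a general rule for all categorical data and sets no denominator. At 20% risk and 20% independent dropout, the three plausible denominators give about 18%, 20% and 22%, so the direction of error is not fixed. Nor is a revised subject's event lost: the adverse event form is completed before termination, so with all enrolled as denominator that subject counts as having a complication.

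The other side can also say that the effect is small. At 20% risk and 10-20% dropout the shortfall is less than one subject in 40, and it falls to 0.25-0.5 points if complications come early. Section VI contains real retention measures (counselling, due listings, escalating contact attempts). The study is uncontrolled and descriptive, and no comparison of complication rates with another series is planned. A 12-month risk is not explicitly named as the target. Finally, Kaplan-Meier does not remove bias if people leave because they are doing badly.

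All of this stands, and it limits the point to a modest one. It does not dispose of it: the plan still leaves the denominator open, allows unequal follow-up, and offers no summary that takes that into account. Adding one costs little.

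**Conclusion.** The concern holds in limited form. Section VII gives complications a frequency and percentage, with no denominator and no treatment of incomplete follow-up, in a study that permits early exit without replacement. If all enrolled subjects are used, 12-month risk is understated: by about 1 to 2 points at 20% risk and 10-20% dropout, and by about 4 points at 30% and 30%. The other denominators either lose subjects terminated because of a complication or overstate the risk.

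It would go too far to conclude that the plan builds in a favourable bias, because that presupposes a denominator it never states.

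The sizes rest on assumed complication and dropout rates, on dropout unrelated to complications, and on a roughly constant hazard; earlier events make them smaller. If subjects at higher risk tend to leave, the understatement could be larger, and the method proposed below would not fully correct it. Sampling error at 30 to 40 subjects outweighs all of these shortfalls. This is a worthwhile improvement to reporting, not a threat to the study.

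**What to change.** In Section VII, for the complications endpoint:

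- Keep the frequency table. State that the unit is the subject and the denominator is all treated subjects, and show the number followed at each visit.
- Add the subject-level cumulative incidence of first complication, and separately of reoperation, at 3, 6 and 12 months from surgery, with 95% confidence intervals and numbers at risk. Use Kaplan-Meier, or Aalen-Johansen with death as a competing event, censoring at last contact.
- State that the estimate assumes dropout is unrelated to complication risk, and tabulate the reasons for early exit so that a reader can judge this.
- Confirm that the CRFs capture the date of each complication and of last contact. Section IX shows that the surgery date is held; the forms in Appendix A are not reproduced, so the other dates could not be checked.

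The cost is a few sentences of plan text and slightly more analysis. No new visits are needed, and no new data if those dates are already recorded. The intervals will be wide at 30 to 40 subjects, and the complication figure may be slightly less favourable than a crude percentage.
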